3.7 Radiography

Radiographs will be taken using a modified Rinn system in order to obtain radiographs with minimum projection error. Rinn system is a radiograph sensor holder that favors a standard system to have reproducible radiograph images. We will customize this holder in order to reproduce standard radiographic image. Evaluable bitewings radiographs will be taken in each of the tooth regions included in the study.

3.7.1 Exposure

Intraoral film, 24 x 40 mm, from the same batch will be used.

3.7.2 Processing

Digital X-ray system will be used.

3.7.3 Handling

Study radiographs are stored in Axium system.

3.7.4 Radiographic assessment

Intra-oral biewing radiographs will be obtained at baseline, at 6 and 12 months. These radiographs should be taken using device to standardize during course of the study and should image the target tooth and at least 2 mm on either side of the osseous defect.

The following standardizing technique will produce repeatable diagnostic quality radiographs with close to identical geometry and image clarity.

Once the exposure parameters are selected they should not be changed during the course of the study. Send the image files to the central reading center at each study site for analysis following the instructions.

3.7.5 Derivation or calculation of variable

Image processing software is used to capture measurements (MiPACS Dental Enterprise). Measurement tool will be calibrated with a 1 millimeter radiographic image.

The measurements are taken from a stationary landmark (Distal and Mesial portion of implant platform - Bd_p and Bm_p) to the mesial and distal bone crest of osseous defect in millimeters (Bd_a and Bm_a). In order to calculate percentage of bone fill (or residual defect) this last measured will be compared with implant length noted on the chart.

Subsequent images are logged in and saved to the file. Linear measurements of bone height along root surfaces are made using the same method as the original defect.

- Linear bone change (distal) = $Bd_{p(0,6,12)} - Bd_{a(0,6,12)}$
- Linear bone change (mesial) = $Bm_{p(0,6,12)} - Bm_{a(0,6,12)}$

Where $(0,6,12)$ is the measure at baseline, 6 and 12 months.

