considerable bone regeneration and re-osseointegration can be obtained by using various types of bone graft materials and membranes. Meta-analysis of latest systematic literature review²² revealed that the weighted mean of marginal bone level change was 1.97 mm, PD reduction was 2.78 mm and BOP reduced by 52.5% by treatment with regenerative treatment. However, a different compatibility between bone grafting material and chemically and mechanically decontaminated implant surface might bring a different clinical outcome. The purpose of the study is to assess the effectiveness of in-situ hardening β - TCP material, easy-graft CLASSIC, for the regenerative treatment of peri-implantitis with polylactide based biodegradable membrane (GUIDOR® Bio-resorbable Matrix Membrane) following clinically adequate decontamination procedures.

The day of surgery will be designated as Day 0. Subjects will have periodontal surgery based on the protocol of Guided Bone Regeneration. Subjects will have a guided bone regeneration surgery with GUIDOR® Bio-resorbable Matrix Membrane and Easy graft classic for the implants experiencing peri-implantitis. The surgical side will be assessed for osseous and implant surface anomalies. Intraoperative and postoperative measurements will be made and the flap will be closed with sutures.

²² Daugela P, et al. (2016) Surgical regenerative treatment for peri-implantitis: Meta-analysis of recent findings in a systematic literature review. J Oral Maxillofac Res. 9 (3): e15

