3.2.1 Primary Efficacy Endpoints

- Change from baseline in probing depth
- Change from baseline in clinical attachment level
- Change from baseline in width of the keratinized tissue
- Change from baseline in radiographic a) bone gain; b) pathology
- Esthetic satisfaction from baseline to six months of all treated areas, as assessed by both the examiner and the subject using the Visual Analog Scale (VAS), prior to and after viewing baseline photos

- Subject pain/discomfort questionnaire

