3.3 Subject Eligibility

3.3.1 Inclusion Criteria

Subjects must meet the following inclusion criteria to be eligible for the study:

1. Subject has read and signed the IRB approved consent form before treatment.
2. Subject must be age 21 or above.
3. Subject must be willing and able to follow study procedures and instructions.
4. Subject affected by moderate to severe peri-implant disease*.
5. Treated chronic periodontitis and proper periodontal maintenance care,

Dental implant must meet the following criteria to be selected for the study:

1. Implant presenting PD \geq 6 mm
2. Radiographic implant bone loss more than 25% of the implant length (Apex of the implant to implant platform)²³.
3. Peri implant bone defect being a buccal dehiscence and semicircular bone resorption to the middle of the implant body, buccal dehiscence and circular bone resorption with lingual bone plate intact or circular bone resorption with buccal and lingual bone plates intact

²³ Froum SJ, Rosen PS. A proposed classification for peri-implantitis. *Int J Periodontics Restorative Dent.* 2012 Oct;32(5):533-40.

CONFIDENTIAL AND PROPRIETARY INFORMATION OF Creighton University School of Dentistry Department of Periodontics

Protocol Number: CUSD2

Revision: October 22nd 2018

Original Issue Date: January 6th 2017

4. Single tooth implant restoration or implant supported fixed partial denture.

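### Section 3.7.5 sets the image scale on a 1 mm reference and leaves the charted implant length unused for scaling, which can magnify marking error in the bone-level measurements

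*Combined protocol and SAP*

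**What the plan says.** Section 3.7.5 (Derivation or calculation of variable) describes the radiographic measurement. On scale it says only: "Measurement tool will be calibrated with a 1 millimeter radiographic image". Distances run from the implant platform "to the mesial and distal bone crest of osseous defect in millimeters", separately on each side. For percentage bone fill, the measured distance is "compared with implant length noted on the chart". That is the only use made of the implant length.

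The section does not say whether the 1 mm reference is a single object or a grid. Nor does it say whether calibration is done once or for each image, or how much marking error is acceptable.

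The outcome affected is one of six listed in section 3.2.1: "Change from baseline in radiographic a) bone gain; b) pathology". Section 3.7.4 says the images "should image the target tooth and at least 2 mm on either side of the osseous defect". Sections 3.7 (Radiography) and 3.7.4 specify bitewings, a customised sensor holder and constant exposure settings.

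**The concern.** A scale set on a short reference turns a fixed marking error into a large relative error, and that relative error carries into every distance measured on that scale. A longer object of known size would dilute it. The study already records such an object, the implant itself, and eligibility in section 3.3.1 is already defined on implant length from apex to platform.

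At stake is the precision of the radiographic bone endpoint, or its calibration bias if one scale is shared by all visits. Percentage fill is also exposed. It divides a scaled distance by a true length, so a scale error does not cancel.

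**Working it through.** The plan gives no measurement-error figure, SD or sample size calculation, so there is nothing of its own to reproduce. What follows is simple error propagation.

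**Inputs from the documents**
- Calibration reference: 1 mm (section 3.7.5).
- Benchmark change: 1.97 mm. Section 2.0 reports that "the weighted mean of marginal bone level change was 1.97 mm" in a cited meta-analysis; it is not a design assumption of this study.
- Size: 15 subjects and at most 20 implants (synopsis).
- Baseline bone loss: more than 25% of implant length (section 3.3.1).

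**Assumptions, not in the documents**
- Marking error e on the reference length: 0.05, 0.1 or 0.2 mm.
- Implant length: 8 to 12 mm, with 10 mm as the working case.
- Baseline bone level B0: 2.5 to 5 mm (2.5 mm is 25% of 10 mm).
- Follow-up level: B1 = B0 − 1.97 mm.

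**Step 1. Relative scale error, r = e/L.** On 1 mm, r is 5%, 10% or 20%. On 10 mm, it is 0.5%, 1% or 2%. For the same e, the ratio is L/1, that is 8 to 12 for implants of 8 to 12 mm.

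**Step 2. One calibration shared by all visits: error in change = r × 1.97.**

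**Step 3. Each image calibrated separately: SD of change = r × √(B0² + B1²).** For B0 = 2.5, √(2.5² + 0.53²) = 2.556. For B0 = 5, √(5² + 3.03²) = 5.846.

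| e (mm) | Reference | Shared (mm) | Separate, B0 = 2.5 (SD, mm) | Separate, B0 = 5 (SD, mm) |
|---|---|---|---|---|
| 0.05 | 1 mm | 0.10 | 0.13 | 0.29 |
| 0.1 | 1 mm | 0.20 | 0.26 | 0.58 |
| 0.2 | 1 mm | 0.39 | 0.51 | 1.17 |
| 0.05 | 10 mm | 0.010 | 0.013 | 0.029 |
| 0.1 | 10 mm | 0.020 | 0.026 | 0.058 |
| 0.2 | 10 mm | 0.039 | 0.051 | 0.117 |

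**Step 4. Add landmark error on the bone level.** Take e = 0.1 mm at each of two visits, which gives 0.1 × √2 = 0.141 mm, and B0 = 5 mm.
- Separate calibration on 1 mm: √(0.141² + 0.585²) = 0.60 mm.
- Shared calibration on 1 mm: √(0.141² + 0.197²) = 0.24 mm.
- Each image scaled on a 10 mm implant: √(0.141² + 0.058²) = 0.15 mm.

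**Step 5. Averaging over subjects.** Separate calibration errors shrink in the mean. With one implant in each of 15 subjects, e = 0.1 and B0 = 5, 0.585/√15 = 0.15 mm. A shared calibration error is a common multiplier and does not shrink at any sample size.

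**Step 6. Percentage measure.** Take a true distance of 5 mm on a 10 mm implant, which is 50%. A 10% scale error reads 5.5/10 = 55%. If the same image is scaled on the implant, the result is a ratio of two lengths in one image, so uniform magnification cancels. A 1% marking error then gives 50.5%.

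**The case against.** A reader might infer that the bone change will be badly wrong. For example, with e = 0.1 mm, a baseline of 4.0 mm and separate calibrations, 0.1 × √(4.0² + 2.03²) = 0.449 mm, or 23% of 1.97 mm. The documents do not support that as the expected error. They give neither the marking error nor the baseline level, and they do not say that images are calibrated separately. With one shared calibration and the same e, the error is 0.20 mm, or 10%. It is then proportional to the change, so it alters neither the sign nor a paired test statistic.

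The phrase about a 1 mm image could also describe a grid marked over many millimetres, in which case most of the penalty goes. And bone-crest landmark error remains whichever scale is used. All of this stands and limits the size of the point.

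A reader might also infer that the whole implant is visible in every image. The requirement to show the target tooth makes this plausible. However, the images are bitewings, and nothing expressly requires platform-to-apex coverage at each visit. This objection also stands, and it shapes the fix: falling back to another reference at one visit only would mix two scales within one change score.

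Finally, the holder and constant exposure settings are said to handle image differences. They do help with projection geometry between visits. They do not remove error made in setting the measuring scale. The examiner calibration in section 3.3.3 concerns clinical recession depth, not radiographs.

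**Conclusion.** The point holds as a modest one. The plan scales on 1 mm and does not use a longer known length that it already records. If the reference is a single 1 mm object, the scale error is 8 to 12 times what an 8 to 12 mm implant would give.

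In absolute terms the result depends on the assumed inputs. The range runs from 0.10 mm (shared calibration, e = 0.05 mm) to an SD of 1.17 mm per site (separate calibration, e = 0.2 mm, B0 = 5 mm). The practical gain also depends on how calibration is done now. At e = 0.1 mm and B0 = 5 mm, total error falls from 0.60 to 0.15 mm if images are calibrated separately, but only from 0.24 to 0.15 mm if one calibration is shared.

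The small sample is not the root of the problem. Separate errors partly average out over 15 subjects, and a shared error would persist in a trial of any size.

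**What to change.** Amend section 3.7.5 as follows.
- State what the 1 mm reference is and how often the tool is calibrated.
- Scale each 0-, 6- and 12-month image on the charted implant length, platform to apex, where both ends are visible at all of that implant's visits.
- Where they are not, use one named fallback reference for all visits of that implant, so that no change score mixes two scales.
- Keep the 1 mm reference as a check, and report repeat-measurement error for the radiographic readings.

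The cost is slightly more measurement work per image. No new visits, images or software are needed, and stored radiographs can be rescaled. The limitation is that some bitewings may not show the apex, so some implants will rely on the fallback; their number should be reported.

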3.0 STUDY DESIGN

3.1 Overall Study Design

This study will be case series, with two periodontists and an examiner. Both of the periodontists will perform surgical procedures and record surgical measurements. The blinded examiner will perform all other clinical assessments. 15 subjects will be enrolled. Written informed consent will be obtained from each subject prior to any study related procedures.

The study will follow subjects for safety and efficacy for 6 and 12 months after their surgical treatment.

Screening will take place no more than 32 days prior to the first treatment and will include the clinical assessments required to confirm eligibility. Clinical photograph, radiographs of the implant treated, clinical measurements will be taken and recorded (Pocked Depth, Mucosal Recession, Clinical Attachment Level). Two to four (2-4) weeks prior to the first study treatment, subjects may undergo plaque removal and root planing and scaling to the areas to be treated, if appropriate. Also, they will receive personalized oral hygiene instructions to reach full-mouth plaque score (FMPS) <20% and full-mouth bleeding score (FMBS) <20%, which will be considered requirement for surgery to occur.

The day of surgery will be designated as Day 0. Subjects will have peri-implant regeneration surgery.

If possible, implant crown will be removed with attention not to damage it. Healing screw will be placed on the implants. Upon flap elevation and debridement of the peri implant lesion, the operator will record the type of bony defect associated to the treated implant (see Inclusion criteria 3). Titanium Implant surface will be debrided with rotating burs and brushes (PERI-SET Swden&Martina Inc.), and decontaminated with EDTA gel (Straumann® PrefGel. pH neutral, 24% EDTA) for 2 minutes and with the alternation of Perio-Flow Chlorhexidine mouthwash (GUM® ParoEx®, Chlorhexidine Gluconate Oral Rinse USP 0,12%, SUNSTAR) saline water and H₂O₂ using cotton pellets. After the completion of these procedures, Easy-graft® CLASSIC will be placed to fill the peri-implant defect.

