3.3.4 Blinding and Probe Calibration

All study staff, with the exception of the treating clinician will be blinded to the treatment administered. Only calibrated UNC 15 probes will be used.

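### The only stated blinding is to a treatment that every subject receives, and the text does not mask radiograph readers to visit, date or order

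*Combined protocol and SAP*

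**What the plan says.** On design, section 3.1 states "This study will be case series, with two periodontists and an examiner". Section 2.0 gives every subject the same intervention: "Subjects will have a guided bone regeneration surgery with GUIDOR® Bio-resorbable Matrix Membrane and Easy graft classic for the implants experiencing peri-implantitis".

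On blinding, section 3.3.4 states "All study staff, with the exception of the treating clinician will be blinded to the treatment administered". Section 3.1 adds "The blinded examiner will perform all other clinical assessments" without saying what that examiner is blinded to. Time point is not mentioned in either place.

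On the endpoint, section 3.2.1 lists "Change from baseline in radiographic a) bone gain; b) pathology" among the primary efficacy endpoints, and section 3.7.4 sets the time points: "radiographs will be obtained at baseline, at 6 and 12 months".

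On reading, section 3.7.4 sends image files to a reading center, described both as central and as located at each site, for analysis under instructions that are not reproduced. Section 3.7.3 names the storage system. Section 3.7.5 names the software, the calibration of the measuring tool and the platform landmark, and then says of follow-up films "Subsequent images are logged in and saved to the file" and "Linear measurements of bone height along root surfaces are made using the same method as the original defect". Sections 3.7 (Radiography) to 3.7.5 name no reader and contain no step that removes date or visit, randomises order or repeats readings. Examiner calibration in 3.3.3 concerns recession depth only.

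**The concern.** With one arm, knowing the treatment cannot distort a comparison between treatments, because there is none. What can distort a before-after comparison is knowing which film came before surgery and which came after. A reader who expects bone gain may place the crest slightly more coronally on a film known to be a follow-up.

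In a controlled trial with masked allocation, a shift common to both arms would largely cancel in the between-arm difference. Here it goes straight into the estimated effect. The stated blinding rule can be followed to the letter and this route to bias stays open.

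The success definition in section 1.0 is also exposed. It requires that there be no further bone loss, with no millimetre tolerance, so an implant whose true change is near zero could be reclassified by a small shift in reading.

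**Working it through.** The plan states no reader error, standard deviation, test, alpha or power for this endpoint, so there is no planned figure to reproduce. The core of the point rests on the text; the arithmetic only shows scale.

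**1. What the stated blinding conceals.** One treatment (2.0, 3.1) combined with blinding to treatment (3.3.4) hides nothing that varies between the films being compared. The item that does vary, the visit, is not masked anywhere in the text.

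**2. How a reader shift enters the estimate.** Take change as the difference between the platform-to-crest readings at two visits. If follow-up films are read with an average favourable shift *b*, then

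expected observed mean change = true mean change + *b*.

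There is no second arm from which to subtract *b*, and enrolling more subjects does not reduce it.

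**3. Scale against the literature figure.** Section 2.0 cites a weighted mean marginal bone level change of 1.97 mm. The shifts are assumed:

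- 0.2 / 1.97 = 0.10, or 10%
- 0.5 / 1.97 = 0.25, or 25%

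**4. Scale against a test.** Assume 15 independent subjects (3.1), no true change, and a two-sided one-sample t-test at an assumed 5% level. The noncentrality is (*b* / SD) × √15; for example, *b* = 0.25 mm and SD = 1.0 mm give 0.25 × 3.873 = 0.97. The chance of declaring a change that is not there, 5% without bias, becomes:

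| Assumed SD of change | *b* = 0.10 mm | *b* = 0.25 mm | *b* = 0.50 mm |
|---|---|---|---|
| 0.5 mm | 11.2% | 43.8% | 94.9% |
| 1.0 mm | 6.5% | 14.7% | 43.8% |
| 1.5 mm | 5.7% | 9.2% | 22.5% |

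Shifts of this size could produce an apparent modest effect. They could not alone account for a change as large as 1.97 mm.

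**5. Why the baseline film needs its own endpoint reading.** Bone loss above 25% of implant length is an entry criterion (3.3.1), and baseline radiographs are among the eligibility assessments (3.6.1). A baseline reading is therefore made before any follow-up film exists, and it is necessarily unmasked. The plan does not separate it from the endpoint reading. If it is reused, a second problem is added: selecting on a threshold favours readings whose error overstates loss, so later readings tend to look better. A fresh masked reading removes the reader's part of that error, though not any error in the film's geometry.

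**6. Workload of a masked reading.** At most 20 implants (synopsis) × 3 time points = 60 image sets; 20% of 60 = 12 repeat readings.

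**The case against.** A reader might infer from 3.7.5 that films are read in sequence with the time point in view. The documents do not say this. The section describes saving files and using a consistent method; the wording is chronological, but it does not say when the readings are made, in what order, or whether the reader sees dates or earlier values. The reading instructions mentioned in 3.7.4 might cover masking. That objection stands, and the point is limited to what it leaves: the visible text provides no masking.

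It can also be said that measurement variation is already controlled by a customised film holder, fixed exposure settings, a calibrated tool and a fixed landmark. These limit random error and may limit how far a reading can plausibly drift, but they do not hide the visit.

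Masking will be imperfect. Graft material may show on follow-up films. Under 3.4.2 the crown is removed and a healing screw placed where possible, with second-stage surgery at 6 months for submerged implants, so the components visible may give away the visit. It would therefore be wrong to claim that 6- and 12-month films can be fully masked. Partial masking still removes date, file order and earlier values from view.

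Finally, probing and the examiner's esthetic score have the same gap and may be more open to expectation. That is fair. Radiographs, however, are stored and can be presented again in masked form, which chairside probing cannot.

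**Conclusion.** The point holds as a weakness in the measurement design. The only blinding stated has no content in a single-arm series, and nothing in the text protects the radiographic primary endpoint from reader expectation. The documents do not show that bias will occur, nor its size or direction. The 10% to 25% figure rests on an assumed shift of 0.2 to 0.5 mm set against a literature mean that is not a planning value for this study. The false-positive rates rest on an assumed SD, shift and test. The conclusion would change if the reading instructions referred to in 3.7.4 already require masking to visit and order; in that case the remedy is to bring that requirement into the protocol. The issue should be corrected because the remedy is cheap, but it does not invalidate the study.

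**What to change.** Keep 3.3.4 as it is, since it is the only general blinding statement and covers all staff. Add to 3.7.5 wording to this effect:

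- Endpoint readings are made after the last month-12 image has been obtained, with date and visit removed and all images in random order.
- They include a new reading of each baseline image, separate from the reading used for eligibility.
- One reader from existing staff, who is not a treating surgeon, makes all of them.
- A random 20% of images are read again and the intra-reader error is reported.
- The report states as a limitation that graft, crown or healing screw, and second-stage status may reveal the visit.

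Section 3.7.4 should also make clear whether reading is central or at each site, so that the reader can be identified.

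The cost is renaming and shuffling at most 60 image sets, about 12 repeat readings, and reading baseline films twice. Endpoint readings are not available until the end of the study. Eligibility readings and any readings made for patient care are unaffected, and no extra films or visits are needed.

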	Assigning Relationship of Adverse Events to Treatment.....	48
	Serious Adverse Events	49
	Definition of a Serious Adverse Event.....	49
	SAE report to Sponsor and IRB	50
5.0	STATISTICAL AND ANALYTICAL PLAN	51
	Intent to Treat Population	51
	Safety Population	51
	Evaluable Population	51
	Missing Data	52
	Assessment of Safety	53
6.0	REGULATORY AND ADMINISTRATIVE REQUIREMENTS.....	53
6.1	IRB Requirements.....	53
6.2	Protocol Amendments	54
6.3	Informed Consent.....	55
APPENDIX I:	QUESTIONNAIRES/SURVEYS	56

PROTOCOL SYNOPSIS

Protocol Number	1015456
Title	A STUDY TO DETERMINE EFFICACY OF EASY GRAFT CLASSIC FOR THE TREATMENT OF PERI-IMPLANTITIS
Subject Population	Subjects with history of Moderate to Severe Peri-implantitis
Objectives	TO ASSESS THE EFFECTIVENESS OF EFFICACY OF EASY GRAFT CLASSIC
Number of Subjects	Maximum of 15 subjects
Number of Sites	Maximum 20 implants
Safety Endpoints	Assessments of subject safety will be based upon tabulations of the incidence of adverse events.
Efficacy Endpoints	
Stability and health of the attachment apparatus at 6 and 12 months by measuring:
 
 • Change from baseline in probing depth • Change from baseline in clinical attachment level • Change from baseline in width of the keratinized tissue • Change from baseline in radiographic A) bone regeneration ; B) pathology • Esthetic satisfaction from baseline to 12 months, as assessed by both the examiner and the subject using the Visual Analog Scale (VAS), prior to and after viewing baseline photos • Subject pain/discomfort questionnaire

CONFIDENTIAL AND PROPRIETARY INFORMATION OF Creighton University School of Dentistry Department of Periodontics

Protocol Number: CUSD2

Revision: October 22nd 2018

Original Issue Date: January 6th 2017

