The authors of this present study considered the outcome of the peri-implant surgical therapy successful if: implant survival with no peri-implant probing depths (PD) \geq 5 mm, with concomitant bleeding on probing (BOP) and no suppuration, in addition to no additional or progressive bone loss. If these criteria were met, it can be assumed that no further intervention other than nonsurgical maintenance care would be required, and the treatment outcome would therefore be regarded as successful.

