The preliminary phase of the study will comprise completion of medical and dental histories, signing of consent forms, obtaining radiographs and photographs, performing screening assessments to confirm eligibility, and instruction in oral hygiene techniques. Before the periodontal surgical procedure, subjects may undergo plaque removal, then root planing and scaling to the areas to be treated, if such treatment is indicated. The final esthetic outcome of the treated sites will be evaluated by the patients using the Visual Analog Scale (VAS) ranging from "Very Unsatisfied" to "Very Satisfied" (before and after viewing baseline photos). Other clinical assessments will include: subject pain/discomfort questionnaire, change in probing depth, change in clinical attachment level, change in width of keratinized tissue from baseline to 6 and 12 months and change in radiographic bone gain and pathology. Digital photographs will be obtained at each study visit and radiographs of the test sites will be made at the baseline, 6 and 12 month visits.

The primary efficacy parameters will include:

- Esthetic satisfaction from baseline to six months of all treated areas, as assessed by both the examiner and the subject using the Visual Analog Scale (VAS), prior to and after viewing baseline photos
- Subject pain/discomfort questionnaire
- Change from baseline in probing depth (PD) measured from the mucosal margin to the bottom of the probeable pocket

- Gingival recession (Rec) measured from the implant platform (IP) to the mucosal margin
- Change from baseline visit in clinical attachment level (CAL) measured from IP to the bottom of the probeable pocket
- Change from baseline in width of the keratinized tissue (KT)
- Change from baseline in radiographic a) bone gain; b) pathology

INVESTIGATIONAL DEVICE

GUIDOR® easy-graft® CLASSIC

GUIDOR® easy-graft® CLASSIC is bone grafting system contains: syringe containing betatricalcium phosphate (β -TCP) granules coated with poly (lactide-co-glycolide) (PLGA) and ampule containing BioLinker® Activator (N-methyl-2-pyrrolidone and water).

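### Section 3.7.5 labels a single-visit bone level as linear bone change, and its bone-fill percentage, compared with implant length, does not measure fill

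*Combined protocol and SAP*

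**What the plan says.** Section 3.7.5 describes the radiographic reading: "The measurements are taken from a stationary landmark", namely the mesial and distal edges of the implant platform (subscript p), to the bone crest of the defect (subscript a), in millimetres. It then gives "Linear bone change (distal) = $Bd_{p(0,6,12)} - Bd_{a(0,6,12" and a mesial formula of the same form. The index (0,6,12) is explained as the measure at baseline, 6 and 12 months, and it is attached to both terms.

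The same section adds a percentage: "In order to calculate percentage of bone fill (or residual defect) this last measured will be compared with implant length noted on the chart". No ratio is written. For later images it says "Linear measurements of bone height along root surfaces are made using the same method as the original defect".

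The endpoint these measurements serve is a difference between visits. Sections 2.0, 3.2.1 and 3.5.2 place it among the primary efficacy measures; Section 2.0 words it as "Change from baseline in radiographic a) bone gain; b) pathology". The Protocol Synopsis has "Change from baseline in radiographic A) bone regeneration ; B) pathology" under the lead-in "Stability and health of the attachment apparatus at 6 and 12 months by measuring". The success definition in Section 1.0 also requires a comparison over time: "in addition to no additional or progressive bone loss". Section 5.0 gives no further derivation of the radiographic variable.

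**The concern.** The section that is meant to turn measurements into the analysis variable never subtracts one visit from another. Both terms of the formula belong to the same visit, so the result is where the bone stands at that visit. The formula is even given for month 0, where a change from baseline must be zero but the formula returns the whole baseline bone loss.

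Followed literally, an implant that has not healed shows the same non-zero 'change' at every visit, and implants with identical gain show different 'changes' because they started with different loss. The sign convention for gain is not stated either.

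The percentage has a related problem. Fill and residual defect run in opposite directions, so one unwritten comparison cannot be both. A comparison of one visit's distance with implant length makes no use of the baseline defect, so it cannot say how much has been filled.

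**Working it through.** The plan states no figure for this variable, so there is nothing to reproduce. The check evaluates the formula as printed.

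**Inputs**
- Formula, landmark and visit index: Section 3.7.5.
- Example gain of 1.97 mm: the literature mean for marginal bone level change in Section 1.0, used only for illustration.
- Entry threshold of more than 25% of implant length: Section 3.3.1.
- Assumed, not in the documents: implant length (10 mm, with 8 and 12 mm as variants) and baseline loss (4 mm, with 3 and 5 mm as variants).

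**Step 1: the formula.** Let L(t) be the platform-to-bone distance at month t. Then |p(t) − a(t)| = L(t). Only the size is shown, because the sign depends on the axis chosen. The change that the endpoint needs is L(0) − L(12).

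| Case | Formula at month 0 | Formula at month 12 | Change from baseline |
|---|---|---|---|
| 4 mm loss, 1.97 mm gain | 4.00 | 4.00 − 1.97 = 2.03 | 1.97 |
| 4 mm loss, no healing | 4.00 | 4.00 | 0 |
| 3 mm loss, 1.97 mm gain | 3.00 | 3.00 − 1.97 = 1.03 | 1.97 |
| 5 mm loss, 1.97 mm gain | 5.00 | 5.00 − 1.97 = 3.03 | 1.97 |

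The same 1.97 mm gain therefore appears as 1.03, 2.03 or 3.03 mm depending on where the implant started. If the entry criterion is measured from the platform, an eligible 10 mm implant has a baseline 'change' above 25% × 10 = 2.5 mm in size.

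**Step 2: the percentage.** The distance just measured, L(t), is compared with implant length. The two direct readings are L/length and its complement. For a 10 mm implant with 4 mm baseline loss:

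| State | L/length | Complement |
|---|---|---|
| No fill | 4/10 = 40% | 60% |
| After 1.97 mm gain | 2.03/10 = 20.3% | 79.7% |
| After 1 mm further loss | 5/10 = 50% | 50% |

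L/length falls when bone is gained and rises when it is lost, so it is residual loss as a share of the implant. The complement moves in the right direction but is remaining bone support, and it stands at 60% when nothing has filled. Both readings also depend on implant length: with 4 mm loss and no fill, an 8 mm implant gives 4/8 = 50% on either reading, and a 12 mm implant gives 4/12 = 33.3% or 66.7%.

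**Step 3: a baseline denominator.** 100 × (L(0) − L(12))/L(0) gives 0% with no healing. With the 1.97 mm gain it gives 1.97/3 = 65.7%, 1.97/4 = 49.25% and 1.97/5 = 39.4% for baseline losses of 3, 4 and 5 mm.

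**The case against.** The strongest reply is that the endpoint lists already say change from baseline, the distances at 0, 6 and 12 months are all recorded from a fixed landmark, and any analyst would subtract. On this view the fault is a mislabelled intermediate variable, and a literal reading gives itself away by reporting a 'change' at baseline. The study is a single-arm case series of at most 15 subjects and 20 implants with no stated test of this variable, so no group comparison or power is affected. The success definition stands in the Background and is not a listed endpoint. Section 3.7.4 also refers to instructions for central reading, which might contain a fuller derivation; the documents do not show.

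Most of this stands as a limit on severity. No data are lost and the intent can be inferred. It does not make the only formula given correct for the endpoint it serves.

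On the percentage, it can be argued that the sentence is too vague to fault, that residual defect is offered as an alternative label, and that gain divided by implant length (1.97/10 = 19.7% in the example) would be zero with no healing. But the sentence compares the distance just measured, not a gain, so that is not its natural reading. What stands is that L/length is a usable index of residual loss, on the same scale as the entry criterion; it is the fill label that fails. The percentage is also not itself a listed endpoint.

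A last point stands in full: the platform-to-bone distance is not shown to equal defect depth, so a percentage with L(0) as denominator should not be called defect fill either.

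**Conclusion.** The concern holds. The expression called linear bone change in Section 3.7.5 is the bone level at one visit and does not yield the change from baseline listed as a primary measure. The percentage compared with implant length is at best residual bone loss, not fill. Both conclusions follow from the algebra and need no assumed values.

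The size is illustrative and rests on the assumed implant length and baseline loss: a month 12 output of 2.03 mm where the change is 1.97 mm, 4.00 mm where the change is 0, and 40% or 60% where fill is 0%. The closeness of 2.03 and 1.97 is an accident of the 4 mm starting value, as the 3 and 5 mm cases show. This should be fixed, but because the measurements allow the right quantity to be computed, it does not threaten the data.

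**What to change.** In Section 3.7.5:

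- Define L(t) as the platform-to-bone distance in mm at month t, mesial and distal, and name the bone point used.
- Relabel the existing formula as bone level at visit t.
- Define bone change as L(0) − L(6) and L(0) − L(12), with positive values meaning gain.
- Report 100 × L(t)/implant length only as residual bone loss in percent of implant length.
- If a percentage of recovery is wanted, use 100 × (L(0) − L(t))/L(0) and describe it as the percentage of the baseline platform-to-bone distance regained.

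The cost is derivation wording only. The same radiographs and measurements serve, and no new data are needed.
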